6. STUDY & TREATMENT PLAN

Study Design

The proposed study will implement a cluster randomized block design where staff are nested within sites. The community-based provider sites and jails will be grouped into homogeneous blocks and then randomly assigned into 2x2 design for each block. The forty-eights sites will be assigned to one of four study arms using a matching strategy within the blocks that groups four jail-clinic combination together prior to randomization. Each jail and CB treatment provider (or clinic) in these combinations will be treated as a site. For instance, if a jail has two post incarceration CB treatment providers (or clinics) in the trial, this will be 3 total sites (of the 48 sites). Within the matching block of 4 jail-clinic combinations, one jail-clinic combination will be randomized to an arm of the study. Twelve sites (that will consist of jails or post incarceration

CB treatment sites) will be assigned to each arm. The number of jails and post-incarceration sites per arm are expected to be balanced, with an anticipated 4 jails and 8 post-incarceration CB provider sites per arm.

Matching will be based on; a) number of clinic sites the jail will be including in the study (as part of the jail-clinic combination), population of the county where the jail is located, and whether or not the jail is currently providing MOUD to CJ population, and if so, what type of MOUD. The blocking procedure will reduce variability within treatment conditions and yield more precise estimates of treatment effects. This strategy will allow for the study team to examine the effects of High versus Low-Dose coaching and ECHO on MOUD use rates in large and small settings. In the study design, there will be a 12-month implementation period followed by 12 months to track sustainability. Data will be collected at baseline, 12 months and 24 months.

[figure not shown]
Intervention

There will be two “scaling-up practices” used in this study; NIATx Coaching and ECHO Clinical Mentoring. The study will look at combination of these two practices to create four intervention study arms;

- 1) High-Dose Coaching/ECHO,
- 2) Low-Dose Coaching/ECHO,
- 3) High-Dose Coaching/No ECHO, and
- 4) Low-Dose Coaching/No ECHO

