Scaling up Practice #1: NIATx Coaching. NIATx framework provides each participating site with a NIATx Coach who is an expert in MOUD implementation and organizational change and will help the organization adopt, implement, and increase the use of MOUD. Coaches help the sites think through key issues, offer process improvement training, and suggest changes. NIATx coaches in the High-Dose and Low-Dose arms will interact with the organization described in Figure 1. The High-Dose coaches will conduct an on-site visit with the site Change Team and complete 11 monthly one-hour calls (months 2-12 of intervention) following the kick-off meeting. Coaches in the Low-Dose arm will hold a one-hour introduction call with the Site Change Team and conduct a two-hour NIATx training via webinar and three quarterly, one-hour calls at months 4, 8 and 12 with the Change Team following the kick-off meeting.

Figure 1: NIATx Coaching (During 12-month Intervention Period)

Step 1. Define Aims: Executive sponsor briefing on project during an in-person Kick-off meeting with Study Team & other Executive Sponsors.

Step 2. MOUD Baseline Assessment: Baseline will include buprenorphine, naltrexone & methadone capacity and Organizational Readiness Baseline Assessment. Assessment and reporting will be completed by Executive Sponsor or an administrator.

Step 3. Train Change Leader & Change Team: One Change Leader and up to 7 members identified by the organization (Change Team) will be trained to implement MOUD during the site visit or introductory call with the site change team.

Step 4. Monitor Progress: Track the number of buprenorphine, naltrexone & methadone capacity and use.

Step 5. Pilot Test Changes to implement MOUD using Plan Do Study Act (PDSA) approach.

Step 6. Sustain Successful Changes: Implement a plan to institutionalize gains to not revert to old ways. Leadership and medical team will be trained to sustain changes made.

Scaling up Practice #2: ECHO. The ECHO model connects MOUD prescribers and experts with primary care providers and medical teams to promote high-quality MOUD practices. ECHO is provided monthly through videoconferences. Experienced MOUD prescribers address topics such as counseling strategies, urine test interpretation, and transitioning from buprenorphine, naltrexone and methadone. Prescribers assigned to the two study arms that include ECHO will participate in 12, one-hour monthly ECHO Videoconferences.

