Physician Satisfaction with MOUD	Modified Physician Worklife Survey	
 • Physician Survey 
 ○ Baseline, 12m, 24m
Implementation		
Organizational Readiness for MOUD	ORIC ³⁹	
 • Organizational Survey 
 ○ Baseline, 12m, 24m
Organizational Climate: Stress	TCU SOF ⁴¹	
 • Staff Survey 
 ○ Baseline, 12m, 24m
Maintenance		
Likelihood of MOUD sustainability	Program Sustainability Assessment Tool ⁴⁰	
 • Staff Survey 
 ○ Baseline, 12m, 24m
NIATx Fidelity & ECHO Fidelity	Organization (using a scale designed for this study)	
 • Organizational Survey 
 ○ Baseline, 12m, 24m

Qualitative Interviews

Qualitative data will be gathered from organizational staff at two points; pre-intervention (baseline) and post-intervention (12 months).

Baseline qualitative phone interviews will be completed with leadership staff at 24 randomly selected sites, six sites within each study arm. Interviews will last approximately 30-45 minutes in length and will be conducted with up to two people at each site. The interviews will be audio-taped (with staff participant permission), but the staff person's identity will be protected and in no way be linked to the results. Interviews will be semi-structured and gather information that is not included within the organizational surveys that will be completed throughout the study. This includes information about site structure and process, culture surrounding justice-involved clients, motivation for serving OUD population and approaches to organizational change. Examples of open-ended questions that will be asked;

1. Please walk me through how a justice-involved client comes to your service?
2. Are your justice-involved clients integrated into your general clientele?
3. Please tell me about the last time your organization made a change to its processes?

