For MOUD and implementation outcomes at 12 month and at 24 month, mixed-effects models (random effects of programs; fixed effects of treatment condition and time) will be used for data analysis. Mixed-effects models, also known as multilevel or hierarchical linear models, are suitable because MOUD patients are nested within programs. Using a multilevel modeling framework, separate models will be applied for the percentage of patients and clinicians using MOUD and their frequency of use (for patients only). Program covariates as well as variables showing noticeable changes between phases will be included in the models as covariates to properly and efficiently estimate the effects of coaching and ECHO. We will examine the coaching and ECHO effects at each time point using cross-sectional multilevel models and will also implement growth curve models across time that include the coaching (high vs. low) and ECHO (present vs. absent) effects, time (baseline, post intervention, follow-up), and interactions between the intervention and time factors, while controlling for relevant time-varying and time-constant covariates. The rates and frequency of MOUD use (by buprenorphine, methadone and injectable naltrexone) and clinical and implementation outcomes will be measured repeatedly for the same programs, and it is expected that these values will be correlated over time. Therefore, instead of assuming independence (i.e., zero correlation) or a compound symmetry covariance structure (i.e., a constant correlation regardless of the proximity of measurement time points), we will allow errors to be auto-correlated or Toeplitz-structured,⁸² denoted as AR(p) or TOEP(p), in the growth curve models. The best-fitting covariance structure will be determined based on heuristic model comparison criteria such as AIC and BIC.

Mediation analysis:

We will examine the mediating effects of organizational factors on MOUD use through: NIATx Fidelity, ECHO Fidelity, the Organizational Readiness for Implementing Change (ORIC), Program Sustainability Assessment, and the Organizational Climate (Stress) measure. These factors will be analyzed using mixed-effects models. Through a mediation analysis, we can estimate the direct (NIATx and ECHO) and indirect effects (Adoption - # of prescribers) of each implementation arm.

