We will test the mediation effect of each potential mediator at each time point as well as across time. The R package 'mediation,' will estimate the causal mediation effects, examine moderated mediation effects, and conduct sensitivity analysis.⁷⁰

Effectiveness analysis:

We will compare MOUD use and retention rates in the 4 different arms using hierarchical linear models, where arm membership is used as the treatment assignment. We will examine the distribution of this outcome measure and will implement an appropriate transformation or nonlinear link function when appropriate (e.g., logistic, Poisson, exponential). Monthly data collection of the Effectiveness as well as Reach (MOUD use) measures, allows for analysis after each stage of NIATx and ECHO.

Table 4: Initiation & Retention

	Data	Source
Initiation	
• # of clients initiated on MOUD• # on MOUD	Organizational Spread Sheet
Retention	
• # of injections• # of weeks on Buprenorphine (30-Day Discontinuation)• # of methadone doses	State Database

Qualitative Analysis:

The qualitative analysis will be conducted by project staff, supervised by the qualitative methodologist, who will ensure that proper and consistent interviewing and analysis techniques are used. Project staff will conduct the interviews, which will be audio recorded and transcribed verbatim. Interviews with leadership personnel will focus on organizational culture, including the organization's approach to making process changes, as well as motivations and expectations for working with justice-involved populations. Interviews with staff will focus on the staff's perspectives on their organizations' experiences with identifying and implementing process changes. Project staff will conduct a directed content analysis of these data. Qualitative data will be summarized and analyzed to detect patterns in individual and clinical approaches to change that have been successful. This description will enhance our understanding of how the NIATx and ECHO models work in criminal justice settings and criminally involved populations, promoting valuable insights that can be applied to future dissemination and implementation of evidence-based practices.

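### ECHO fidelity cannot mediate ECHO versus No ECHO, because half the sites have no ECHO to be faithful to; the other mediation paths are estimable but need a stated time order

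*Combined protocol and SAP*

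**What the plan says.** Section 10, Mediation analysis, names five mediators of MOUD use. It opens "We will examine the mediating effects of organizational factors on MOUD use through: NIATx Fidelity, ECHO Fidelity" and continues with organizational readiness (ORIC), the program sustainability assessment and organizational climate (stress). It then says that "we can estimate the direct (NIATx and ECHO) and indirect effects (Adoption - # of prescribers) of each implementation arm". The number of prescribers is not among the five listed mediators.

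On timing, the same section says "We will test the mediation effect of each potential mediator at each time point as well as across time". Estimation is by an R package for causal mediation, with moderated mediation and a sensitivity analysis. No identifying assumptions, confounder set or ordering of mediator before outcome is given.

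On delivery, Section 6 (Intervention) says "Prescribers assigned to the two study arms that include ECHO will participate in 12, one-hour monthly ECHO Videoconferences". Table 1 shows no ECHO component in the other two arms. All four arms receive NIATx coaching.

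On measurement, Table 2 has a single row for "NIATx Fidelity & ECHO Fidelity", on a scale made for this study, scheduled at baseline, 12 and 24 months. It has no arm restriction and no rule for scoring a No-ECHO site.

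**The concern.** To split an effect into direct and indirect parts, the mediator needs a meaningful value under both levels of the contrast. ECHO fidelity has none at a site that was never offered ECHO: it is either undefined or fixed at zero by assignment. Software may still return a number, which would be read as showing how ECHO works.

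Two timing questions affect all the mediators. A value recorded before the intervention cannot carry its effect. And a mediator surveyed at month 12 or 24, related to MOUD use at that same time, need not precede it: a site that has already raised MOUD use may report higher readiness or sustainability because of that success.

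What is at stake is the account of mechanism in a trial meant to guide scale-up.

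**Working it through.** The plan gives no sample size, power or effect size for mediation, so there is no figure to reproduce. The check concerns what the design can identify.

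**Inputs.** Four arms of 12 sites, 48 in total (Section 6, Data Source). ECHO in two arms: 2 × 12 = 24 sites with ECHO and 24 without. Expected attrition 11% (Section 10, Sample Size & Power). Notation: E = ECHO assignment, C = coaching dose, F = ECHO fidelity, Y = MOUD use.

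**Step 1: F missing at No-ECHO sites.** Complete cases are the 24 ECHO sites. E equals 1 at all of them, so its variance is 0. A design matrix with intercept, E, C and F has rank 3 for 4 columns. Neither the effect of ECHO nor its indirect path can be estimated.

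**Step 2: F coded zero at No-ECHO sites.** Take Y = α + βE + γC + θF. Setting coaching aside for simplicity, F does not vary among No-ECHO sites, so θ is the fidelity slope among ECHO sites alone. The indirect effect is θ × (mean F at ECHO sites − 0). The direct effect β compares a predicted ECHO site at zero fidelity with the No-ECHO mean. No No-ECHO site has fidelity above zero, so the split rests on extending the within-ECHO line.

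The documents give no fidelity distribution. I assume a 0-1 scale with mean 0.8 at ECHO sites and a range of between-site SDs, simulated for 48 sites with values truncated to 0-1:

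| Assumed SD | Correlation of F with E | Variance inflation, 1/(1 − r²), median |
|---|---|---|
| 0 | 1 | infinite |
| 0.05 | 0.996 | 139 |
| 0.10 | 0.986 | 37 |
| 0.20 | 0.956 | 12 |
| 0.30 | 0.917 | 6.6 |

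Without truncation, r = μ/√(μ² + 2σ²). At SD 0.10 this is 0.8/√(0.64 + 0.02) = 0.985, close to the simulated value. At SD 0.30 it is 0.8/√(0.64 + 0.18) = 0.883; truncation narrows the spread and raises the simulated figure to 0.917. If an ECHO-by-fidelity term is added, E × F is the same column as F, and the matrix has rank 4 for 5 columns.

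**Step 3: a mediator measured at baseline.** Under randomization the expected difference in a baseline value between 24 ECHO and 24 No-ECHO sites is 0. In mediator SD units its standard error, treating sites as independent, is √(1/24 + 1/24) = 0.289. Simulation gave mean −0.002 and SD 0.29. Any indirect effect found there is chance imbalance.

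**Step 4: which time points are meant.** Section 6 says "Data will be collected at baseline, 12 months and 24 months", and the growth models in Section 10 list "time (baseline, post intervention, follow-up" as the levels of the time factor. On that reading there are 5 × 3 = 15 cross-sectional mediator tests, 5 of them at baseline. The Intervention and Sustainability text, however, opens "For MOUD and implementation outcomes at 12 month and at 24 month". On that reading there are 5 × 2 = 10, none at baseline.

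**Step 5: what remains available.** Within the ECHO arms there are 12 High-Dose and 12 Low-Dose sites; 24 × 0.89 = 21.4, or about 21 after attrition. C still varies, so ECHO fidelity can be studied there as a dose-response measure or as a mediator of coaching dose. For the other mediators, Section 6 plans monthly tracking at all 48 sites and Section 3 continues Reach collection through months 12-24, so a month-12 mediator can precede later MOUD use.

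**The case against.** The strongest reply is that only one path fails. A reader might infer that none of the plan's indirect effects is identified. The documents do not support that. The indirect path the plan itself names runs through the number of prescribers, which Section 6 collects at all sites at baseline, 12 and 24 months. ORIC, climate and sustainability come from surveys at all sites, and NIATx fidelity can have a value in every arm because every arm is coached. For these paths the gap is one of specification: no ordering, no confounder set, and the number of prescribers missing from the mediator list.

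A reader might also take it as settled that mediation will be tested at baseline. The sentence on time points neither names nor excludes baseline. Including it is the natural reading, but an inference, so the count of 15 tests is conditional.

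Nor does the plan commit itself to same-time testing. MOUD use is tracked monthly, and the Effectiveness analysis text notes that this allows analysis after each stage. Reverse causation is a risk left open by the missing ordering.

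All of this stands, and it narrows the point. It does not rescue ECHO fidelity under the ECHO contrast. The sensitivity analysis is not described, and probing unmeasured confounding would not supply fidelity values where there was no ECHO. Moderated mediation does not supply them either.

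**Conclusion.** The point holds in this limited form. The indirect effect of ECHO versus No ECHO through ECHO fidelity is not identified, because 24 of 48 sites have no meaningful value. That follows from the design and needs no assumption about the data. The collinearity figures (correlation 0.917 to 0.996 for SDs of 0.30 to 0.05) do rest on an assumed mean fidelity of 0.8 on a 0-1 scale and are illustrative.

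Any mediation test at baseline would be uninformative, if the plan intends one. The remaining paths are estimable in principle but under-specified, and same-time tests of them could not separate mediation from reverse causation.

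This is a secondary analysis of mechanism. The randomized comparison on Reach, the primary aim, is unaffected. The change is still worth making: the plan as written would yield an ECHO-fidelity mediation estimate with no interpretable meaning, and the remedy is cheap.

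**What to change.** Amend Section 10, Mediation analysis, as follows.

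- **ECHO fidelity.** Do not use it as a mediator of ECHO versus No ECHO. Analyse it only within the 24 ECHO sites, as a dose-response measure or as a mediator of High versus Low coaching.
- **Time points.** State that mediation is tested only with post-baseline mediators. The baseline fidelity entry in Table 2 can stay on the survey schedule but should not be analysed.
- **Ordering.** For ORIC, climate, sustainability, NIATx fidelity and number of prescribers (added to the list), make the main model the month-12 mediator with MOUD use in months 13-24 from monthly tracking. Adjust for baseline MOUD use and for the baseline mediator where a meaningful one exists. Label same-time analyses as exploratory associations.
- **Assumptions.** State the mediator-outcome confounders adjusted for and what the sensitivity analysis varies.

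The cost is wording; no new data are needed. The downsides are that there is no main mediation estimate for the first 12 months, and that the within-ECHO analyses rest on 24 sites (about 21 after attrition) and will be imprecise. The dose-response version also compares sites on a fidelity level that was not randomized.

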3. STUDY OBJECTIVES

The specific aim of this study is to compare High-Dose NIATx Coaching/ECHO, Low-Dose NIATx Coaching/ECHO, High-Dose NIATx Coaching/No ECHO, and Low-Dose NIATx Coaching/No ECHO. Impact will be measured using the RE-AIM framework:

- *Reach* (primary aim) measured as the percent of eligible justice involved patients who 1) are initiated onto any MOUD (buprenorphine, extended-release injectable naltrexone, or methadone), and 2) engaged with MOUD use.
- *Effectiveness* measured in terms of impact of MOUD involvement on re-arrest rates.
- *Adoption* measured as the percent of eligible clinicians in jail and/or community providers who use MOUD.
- *Implementation* measured by an organizational readiness for MOUD implementation over time and intervention fidelity scale (*for NIATx and ECHO*).
- *Maintenance* measured as the likelihood of organizations sustaining provision of MOUD utilization (organizational sustainability scores at 12 and 24 months of intervention) and we will continue to collect Reach, Effectiveness, and Implementation measures during the maintenance phase (Ms 12-24).

Study Coordination

The UW-Madison Center for Health Enhancement Systems Studies (CHESS) and George Mason University Center for Advancing Correctional Excellence! are the coordinating sites for this study. George Mason holds the grant award for the larger study this research is embedded in. The UW site will oversee all recruitment and study implementation activities which includes:

- developing organizational site-specific recruitment and data collection processes that meet study objectives;
- training staff on protocol procedures prior to start of recruitment and continuous monitoring to assure compliance with the protocol and human subjects regulation;

- communicating with clinic site staff as needed via conference calls to monitor progress, inform of protocol changes/distribute new version of protocol, and address unanticipated issues or challenges;
- manage all study data;
- oversee analysis; and
- oversee publications and presentations.

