The designated Executive Sponsor or the Change Leader at each site will manage staff member recruitment to construct a change team of up to a seven (7) member Change Team. Up to two of the team members will be physicians. Each member of the change team as well as the change leader will be asked to complete staff surveys at baseline, 12m, and 24ms for a total of 8 "staff" surveys per site. Information on the implementation process will be gathered from site staff members during surveys and interviews.

The full Staff Survey including Organizational Readiness for Implementing Change (ORIC), Organizational Climate-Stress, Attitudes toward MOUD and Program Sustainability, will be administered three times during the study (baseline, 12m, 24m). Each survey is expected to take approximately 20 minutes or less to complete. Staff completing the surveys will receive consent documents when they are sent the survey link via REDCap. To increase survey

completion rates for the Staff Surveys, the research team at UW will conduct follow-up phone calls and e-mails with the Change Leaders at Week 1 of post-survey distribution to assure the survey receipt, then at Weeks 4 and 12-post survey distribution if surveys are not complete. Each survey cycle, at months listed above, will include up to 384 people per cycle. The 384 staff will include up to 8 participants from the 48 sites and will include the Change Leader (supervisor/member of the leadership staff), and up to 7 team members part of the Change Team (CJ staff, prescribers, clinicians, nurses, counselors, social workers, etc). Since many of the same staff will likely complete surveys in successive cycles, 536 unique staff are expected for survey completion across all three cycles. The 536 unique people projected assumes 20% or 76 new people per round occurs post-intervention and post sustainability round. There will be a total of 1,152 surveys.

Physician Surveys & Data:

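### The sustainability score is both the Maintenance outcome and a same-wave mediator of MOUD use, so part of a coaching or ECHO effect can be wrongly credited to it

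*Combined protocol and SAP*

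**What the plan says.** Section 3 defines Maintenance as "measured as the likelihood of organizations sustaining provision of MOUD utilization", read from "organizational sustainability scores at 12 and 24 months of intervention". The Maintenance block of Table 2 (Section 6) has a row labelled "Likelihood of MOUD sustainability", measured with the Program Sustainability Assessment Tool in the Staff Survey at baseline, month 12 and month 24. Section 6 (Staff Surveys & Data) gives the same three waves.

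Section 10 (Mediation analysis) then gives the score a second role. It opens "We will examine the mediating effects of organizational factors on MOUD use through" and names five factors: the NIATx and ECHO fidelity scales, "the Organizational Readiness for Implementing Change (ORIC), Program Sustainability Assessment, and the Organizational Climate (Stress) measure". Each is to be tested at every wave and also longitudinally. The R package named there is to give causal mediation estimates and an unspecified sensitivity analysis.

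The section does not say which period of MOUD use is paired with which wave of the score. It does not adjust the mediation model for earlier use or test the reverse path. The same section also describes the indirect effect as running through Adoption (number of prescribers), which is not among the five listed factors.

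**The concern.** A mediator has to come before the outcome it explains. The baseline score precedes the intervention and cannot carry its effect. The month-12 score is collected at the end of the 12 months in which the month-12 MOUD outcome accrued, and the month-24 score stands in the same relation to use up to month 24. Staff at a site that has built up MOUD use have reason to rate its continuation as more likely. A same-wave model cannot tell that path (use to score) from the hypothesised one (score to use). Randomisation protects the arm-to-score and arm-to-use comparisons, but not the link between score and use.

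At stake is the mechanism the trial reports. A finding that coaching or ECHO works by building sustainability could shape later scale-up when the data show only that sites using more MOUD rate themselves as more sustainable. Within the mediation analysis, the direct effect would be too small by the amount wrongly called indirect.

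**Working it through.** The mediation section states no figure, so there is nothing to reproduce. The size of the error follows from a simple model in which sustainability has no effect on use.

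**Inputs from Section 10 (Sample Size & Power).** 42 programs at study end, 75 patients per program, ICC 0.10, coaching effect d = .51. **Assumption.** The within-arm correlation r between score and MOUD use is not in the documents; 0 to .7 is shown.

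**Share falsely mediated.** Let T be arm, Y program-level MOUD use and M the score, with unit residual variances:

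- Y = bT + e
- M = cY + u, with no path from M to Y
- within-arm correlation r = c/√(1 + c²), so c = r/√(1 − r²)

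The mediation model then estimates:

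- arm-to-score path: cb
- coefficient of M in the regression of Y on T and M: c/(1 + c²)
- indirect effect: cb × c/(1 + c²) = b × c²/(1 + c²) = b r²
- direct effect: b(1 − r²)

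The true indirect effect is zero, so the false share is r²:

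- r = .3: 0.09
- r = .5: 0.25
- r = .7: 0.49

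The share depends on neither b nor the number of programs.

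**How often it would look established.** This does depend on b. The plan does not say whether d = .51 is on the program or the patient scale, so both were used. On the patient scale, the program-level effect is .51/√(0.10 + 0.90/75) = .51/√0.112 = 1.52 SD. The simulation used 21 versus 21 programs, 3,000 runs, the product of coefficients and a Monte Carlo 95% interval:

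| r | Mean false share (0.51 / 1.52 SD) | Interval excludes 0, 0.51 SD | Interval excludes 0, 1.52 SD |
|---|---|---|---|
| 0 | 0% / 0% | 0.2% | 0.2% |
| .3 | 9% / 9% | 3% | 14% |
| .5 | 25% / 25% | 12% | 63% |
| .7 | 51% / 50% | 23% | 94% |

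The simulated shares agree with r² to within simulation error. The r = 0 row shows that the false findings come from the reversed path and not from the interval method.

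The simulation is a single two-group contrast at one wave, not the planned 2×2 repeated-measures model. It indicates scale and does not forecast the trial's result.

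**The case against.** **The outcome role alone is not an error.** This stands. A path from sustainability to later MOUD use is a legitimate hypothesis. The tool's items are not shown, and Section 3 describes a forward-looking likelihood. The documents cannot settle how far answers reflect current use.

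**The plan also tests mediation longitudinally.** With three waves of the score and monthly MOUD tracking, a properly ordered analysis is possible. But the plan specifies no lag and no adjustment, and it keeps the same-wave tests as causal. Nor does the sensitivity analysis answer the point. Its content is not stated, and the usual form varies unmeasured confounding while taking the order of mediator and outcome as given.

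**The size rests on an unknown correlation.** This stands. A reader might infer that a false mechanism will be reported. The documents do not support that: if r is near zero, the error is negligible.

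**The score is not alone.** This stands too. ORIC is itself an Implementation measure, and Table 2 puts ORIC and Stress at the same waves, so dropping one mediator would leave the ordering gap for the others. The sustainability score is the clearest case because it rates the continuation of MOUD provision itself.

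A reader might also infer that the coaching and ECHO effects on Reach, the primary aim, are biased. They are not: those models compare randomised arms and do not use the score as a mediator.

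**Conclusion.** The concern holds in bounded form. The same-wave mediation test of the sustainability score cannot separate score-to-use from use-to-score, and nothing in the plan fixes the order. If the score only reflects use, the falsely mediated share is r²: 9%, 25% and 49% at r = .3, .5 and .7. The chance that the 95% interval excludes zero runs from about 3/12/23% to about 14/63/94%, depending on the scale of d = .51. These figures assume no true score-to-use effect, a correlation that the documents do not give, 42 programs and one contrast at one wave. The damage is confined to the direct/indirect decomposition in a secondary, explanatory analysis. It should be corrected, but it does not threaten the main comparisons.

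**What to change.** In Section 10 (Mediation analysis):

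1. Replace the same-wave mediation test of the sustainability score with a time-ordered one: the month-12 score against the site's MOUD use in months 13-24, adjusted for the baseline score and for MOUD use through month 12.
2. Report same-wave relations between score and use as associations only.
3. Apply the same ordering to ORIC and Stress. Section 8 gives two collection points for Stress where Section 6 gives three; confirm that baseline and month 12 are both covered.
4. State the assumptions that remain. Use through month 12 is itself affected by arm, so adjusting for it does not by itself justify a causal direct/indirect split.
5. Reconcile the list of five mediators with the later statement that the indirect effect runs through the number of prescribers.

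Alternatively, take the score out of the mediator list and analyse it only as the Maintenance outcome by arm.

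Either route is a wording change and needs no new data: Section 6 provides monthly MOUD tracking, and Section 3 continues Reach collection in months 12-24. The cost is that mediation of MOUD use in months 1-12 by this score is no longer reported.
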